5.3.2. Safety Data

For the analysis of safety endpoints, the standard rules for imputation according to CaPS will be applied.

6. ANALYSES AND SUMMARIES

6.1. Primary Endpoints

6.1.1. Mass Balance

Individual participant and median data profiles for total radioactivity will be graphically presented for the cumulative recovery of radioactivity in urine, feces and their combination over time in **Cohort 1 only**. Vomitus, if any, will be collected in full during the \square hours after oral dosing in **Cohort 1** and will be required to be prospectively tested for recovered radioactivity. For emesis that occurs after \square hours up to \square hours post dose, samples will be collected in full and stored for potential reflex testing for recovered radioactivity. These participants will not necessarily be excluded from analysis. The total recovery of radioactivity in urine, feces (and vomitus, if any) and their combination will be listed and summarized for **Cohort 1 only**.

6.1.2. Metabolic Profiling and Metabolite Identification

Results of the metabolic profiling analysis will be detailed in a separate report and will be summarized within the CSR.

6.2. Secondary Endpoints

6.2.1. Absolute Oral Bioavailability

Natural log transformed $AUC_{inf}(dn)$ (if data permit) and $AUC_{last}(dn)$ from Cohort 2 will be analyzed using a mixed effect model with treatment as a fixed effect and participant variable as a random effect. Estimates of the adjusted (least squares) mean differences (Test/Reference) and the corresponding 90% confidence interval in log-scale will be obtained from the model. The adjusted mean differences and 90% confidence intervals for the differences will be exponentiated to provide estimates of the ratio of adjusted geometric mean (Test/Reference) and 90% confidence interval for the ratio. IV [^{14}C]PF-07220060 will be considered the Reference formulation and unlabeled oral PF-07220060 will be considered the Test formulation.

6.2.2. Fraction of PF-07220060 Dose Absorbed (F_a)

The ratio (Test/Reference) of the geometric means of % Total ^{14}C in Urine will be estimated. Total $^{14}C_Urine_IV$ is the Reference and Total $^{14}C_Urine_PO$ is the Test.

A distribution-free method (nonparametric method, Hodges-Lehmann point estimate) may be conducted if extreme values are encountered in the PK parameters.

Cumulative urine ^{14}C amounts, percent ^{14}C dose as well as F_a (calculated using urine ^{14}C data, as described above) will be listed by treatment (Oral in Cohort 1 and IV in Cohort 2) and summarized using descriptive statistics. Individual and summary profiles of urine ^{14}C will be graphically presented.

In most circumstances, F_a estimation based on the urine method provides reliable F_a estimates. Total radioactivity following oral and IV administration will be generated from

different people in separate cohorts, where physiological variability may lead to a less robust estimation of F_a . Different F_a calculation methods have been compared in detail and alternative F_a calculation methods for this study may be investigated as needed based on emerging data.

6.2.3. Safety Endpoints

All safety analyses will be performed on the Safety Analysis Set.

Safety data will be presented in tabular and/or graphical format and summarized descriptively by treatment, where appropriate.

6.2.3.1. Adverse Events

Adverse events will be reported in accordance with the CaPS and listed by treatment, where appropriate.

Participant discontinuations due to adverse events will be detailed by treatment. Data will be reported in accordance with the CaPS.

6.2.3.2. Laboratory Data

Laboratory data will be listed and summarized by treatment in accordance with the CaPS.

6.2.3.3. Vital Signs

Vital signs data will be listed and summarized by treatment in accordance with the CaPS.

6.2.3.4. Electrocardiograms

ECG data will be listed and summarized by treatment in accordance with the CaPS.

6.3. Other Safety Summaries and Analyses Endpoint(s)

None.

6.4. Exploratory Endpoints

PK parameters will be summarized descriptively in accordance with Pfizer data standards for the PK Parameter Analysis Set, as data permit. Missing values will be handled as detailed in [Section 5.3.1](#). Each PK parameter will be summarized and will include the set of summary statistics as specified in [Table 4](#).

Table 4. PK Parameters to be Summarized Descriptively

Parameter	Summary Statistics
AUC _{inf} , AUC _{inf} (dn), AUC _{last} , AUC _{last} (dn), C _{max} , C _{max} (dn), CL, CL/F, V _{ss} , V _z /F Ae, Ae%, CL _r	N, arithmetic mean, median, SD, %CV, minimum, maximum, geometric mean and geometric %CV
T _{max}	N, median, minimum, maximum
t _{1/2}	N, arithmetic mean, median, SD, %CV, minimum, maximum

Supporting data from the estimation of t_{1/2} and AUC_{inf} will be listed by analyte and group: terminal phase rate constant (k_{el}); goodness of fit statistic from the log-linear regression (r²); the percent of AUC_{inf} based on extrapolation (AUC_{extrap} %); and the first, last, and number of time points used in the estimation of k_{el}. This data may be included in the clinical study report.

Presentations for plasma PF-07220060, [¹⁴C] and [¹⁴C]PF-07220060 concentrations will include:

- A listing of all concentrations sorted by participant ID, treatment and nominal time postdose. The concentration listing will also include the actual times. Deviations from the nominal time will be provided in a separate listing.
- A summary of concentrations by treatment and nominal time postdose, where the set of statistics will include n, mean, median, SD, %CV, minimum, maximum and the number of concentrations above the LLQ.
- Median concentrations time plots (on both linear and semi-log scales) against nominal time postdose (median concentration-time profiles for plasma PF-07220060, [¹⁴C] and [¹⁴C]PF-07220060 on the same plot per scale, based on the summary of concentrations by time postdose).
- Mean concentrations time plots (on both linear and semi-log scales) against nominal time postdose (mean concentration-time profiles for plasma PF-07220060, [¹⁴C] and [¹⁴C]PF-07220060 on the same plot per scale, based on the summary of concentrations by time postdose).
- Individual concentration time plots (on both linear and semi-log scales) against actual time postdose (there will be separate spaghetti plots per scale for PF-07220060, [¹⁴C] and [¹⁴C]PF-07220060).
- Individual concentration time plots by participant (on both linear and semi-log scales) against actual time postdose [there will be separate plots for each participant (containing all applicable concentration-time profiles) per scale].

6.4.1. Contingent Metabolic Profiling and Metabolic Identification

Results of the metabolic profiling analysis will be detailed in a separate report and will be summarized within the CSR.

6.4.2. Plasma PK Parameters of PF-07220060

Plasma PK parameters of PF-07220060, as appropriate, will be summarized descriptively in accordance with Pfizer data standards for the PK Parameter Analysis Set, as data permit. Each PF-07220060 PK parameter will be summarized by treatment and will include the set of summary statistics as specified in [Table 4](#).

6.4.3. Plasma PK Parameters of [¹⁴C]PF-07220060

Plasma PK parameters of [¹⁴C]PF-07220060 for Cohort 2, as appropriate, will be summarized descriptively in accordance with Pfizer data standards for the PK Parameter Analysis Set, as data permit. Each [¹⁴C]PF-07220060 PK parameter will be summarized and will include the set of summary statistics as specified in [Table 4](#).

6.4.4. Urine PK Parameters of PF-07220060

Urine PK parameters (including Ae, Ae% and CL_r in Cohort 1), will be summarized descriptively in accordance with Pfizer data standards for the PK Parameter Analysis Set, as data permit. Each urine PK parameter will be summarized and will include the set of summary statistics as specified in [Table 4](#).

6.4.5. Plasma PK Parameters of Total Radioactivity [¹⁴C]

Plasma PK parameters of total [¹⁴C] radioactivity, as appropriate, will be summarized descriptively in accordance with Pfizer data standards for the PK Parameter Analysis Set, as data permit. Each total [¹⁴C] radioactivity PK parameter will be summarized by treatment and will include the set of summary statistics as specified in [Table 4](#).

6.4.6. Allelic Variants of Drug Metabolizing Enzymes and Transporters

Allelic variants of drug metabolizing enzymes and transporters will be summarized descriptively.

6.4.7. Taste Assessment Data

The sensory attributes (bitterness, tongue/mouth burn, throat burn) from the Oral Solution or Suspension Palatability Questionnaire will be listed and descriptively summarized by treatment, and question across participants. Summary statistics (mean and 90% CI) will be calculated for the various questions. Radar plots for each of 4 time points (1, 5, 10 and 20 minutes after dosing), summarizing all attributes for each treatment will be generated. Boxplots of each attribute will be plotted against the time points.

6.5. Subset Analyses

There are no planned subset analyses.

6.6. Baseline and Other Summaries and Analyses

6.6.1. Demographic Summaries

Demographic characteristics will be summarized for enrolled population in accordance with the CaPS.

6.6.2. Study Conduct and Participant Disposition

Participants evaluation groups will show end of study participant disposition. Frequency counts will be supplied for participant discontinuation(s) by treatment. Data will be reported in accordance with the CaPS.

6.6.3. Study Treatment Exposure

Study treatment exposure will be listed.

6.6.4. Concomitant Medications and Nondrug Treatments

All concomitant medication(s) as well as non-drug treatment(s) will be reported in the listings.

7. INTERIM ANALYSES

No interim analysis will be conducted for this study. As this is an open-label study, the sponsor may conduct reviews of the data during the course of the study for the purpose of safety assessment, facilitating PK modeling, and/or supporting clinical development.

APPENDICES**Appendix 1. Summary of Analyses**

Endpoint	Population	Data Inclusion and Rules for Handling Intercurrent Events and Missing Data	Analysis Method
Mass balance	Mass Balance Analysis Set	Observed data	Descriptive statistics
Metabolite identification/profiling	PK Concentration Analysis Set	Observed data	Descriptive statistics
Absolute oral bioavailability	PK Parameter Analysis Set	Observed and imputed (Section 5.3.1) data	Mixed effect model
Fraction of dose absorbed	PK Parameter Analysis Set	Observed and imputed (Section 5.3.1) data	Mixed effect model or Hodges-Lehmann point estimate
Safety data	Safety Analysis Set	Observed and imputed (Section 5.3.2) data	Descriptive statistics
PK parameters	PK Parameter Analysis Set	Observed and imputed (Section 5.3.1) data	Descriptive statistics
PK concentrations	PK Concentration Analysis Set	Observed and imputed (Section 5.3.1) data	Descriptive statistics
Taste assessment data	Safety Analysis Set, have at least 1 taste assessment performed	Observed data	Descriptive statistics

Appendix 2. SAS Code for Analyses

An example of PROC MIXED code is provided below.

For absolute oral bioavailability:

```
proc mixed data=tab.pk;  
  class trt participant;  
  model log&var=trt / ddfm=KR;  
  random participant / subject=participant;  
  lsmeans trt;  
  estimate 'B vs A' trt -1 1 /cl alpha=0.1;  
  
  ods 'Estimates' out=est&var;  
  ods 'lsmeans' out=ls&var;  
  ods 'covparms' out=cov&var;  
  ods 'tests3' out=tst&var;  
run;
```

```
/* Letter assignments for treatments (trt) within the estimate statement above are as follows  
A: IV [14C]PF-07220060 (reference)  
B: oral unlabeled PF-07220060 (test)  
*/
```

For fraction of dose absorbed:

```
proc mixed data=tab.pk;  
  class trt participant;  
  model log&var=trt / ddfm=KR;  
  random participant / subject=participant;  
  lsmeans trt;  
  estimate 'B vs A' trt -1 1 /cl alpha=0.1;  
  
  ods 'Estimates' out=est&var;  
  ods 'lsmeans' out=ls&var;  
  ods 'covparms' out=cov&var;  
  ods 'tests3' out=tst&var;  
run;
```

```
/* Letter assignments for treatments (trt) within the estimate statement above are as follows  
A: IV [14C]PF-07220060 (reference)  
B: PO [14C]PF-07220060 (test)  
*/
```

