### Study Arms and Duration:

Study Intervention(s)			
Intervention Name	[  C]PF-07220060	PF-07220060	[  C]PF-07220060
Type	Drug	Drug	Drug
Use	Experimental	Experimental	Experimental
IMP or AxMP	IMP	IMP	IMP
Dose Formulation	Oral suspension	Oral suspension	IV solution
Unit Dose Strength(s)	100 mg	100 mg	CC1 μg
Dosage Level(s)	100 mg, single dose	100 mg, single dose	CC1 μg, single dose
Route of Administration	Oral	Oral	IV infusion

Study Arm(s)		
Arm Title	Cohort 1	Cohort 2
Arm Type	Experimental	Experimental
Arm Description	Oral dose of 100 mg PF-07220060 containing CC1 nCi [  C] ([  C]PF-07220060) will be administered as an extemporaneously prepared liquid formulation.	Unlabeled oral dose of PF-07220060, 100 mg will be administered as an extemporaneously prepared liquid formulation. Approximately 2 hours after the administration of the unlabeled oral dose, a single dose of CC1 μg PF-07220060 containing CC1 nCi [  C] ([  C]PF-07220060) will be administered IV, as an infusion over approximately 30 minutes
Associated Intervention Labels	[  C]PF-07220060	PF-07220060, [  C]PF-07220060

This will be a parallel-cohort study including 2 independent cohorts without crossover. Cohort 2 will be enrolled approximately 15 days after Cohort 1 enrollment. Eligible participants will be admitted to the clinical research unit (CRU) on Day -1. In Cohort 1, participants will receive a single oral dose of 100 mg [C]PF-07220060 containing approximately CC1 nCi on Day 1. Blood, urine, feces, and vomitus (if any) will be collected over predefined intervals. Participants dosed in Cohort 1 will be eligible for discharge between Days 5 to 14 when at least one of the 3 following criteria are met: (1) ≥90% of the administered radioactive dose has been recovered in urine+feces+vomit (if any); (2) <1%

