In Cohort 2, urine samples will also be collected at pre-specified intervals as described in the SoA and total radioactivity excreted in urine following intravenously administered [ $^{14}\text{C}$ ]PF-07220060, will be measured via AMS. The ratio of dose-normalized total radioactivity recovered in urine following oral administration of [ $^{14}\text{C}$ ]PF-07220060 in Cohort 1 to that recovered in urine following IV administration of [ $^{14}\text{C}$ ]PF-07220060 in Cohort 2 will estimate the  $F_a$  following oral administration of [ $^{14}\text{C}$ ]PF-07220060. Note, IV and oral radioactivities will be collected from participants in different cohorts. Also, this calculation of  $F_a$  assumes that metabolites generated during first pass are not renally eliminated and that parent drug excretion in urine is minimal for drugs that undergo first pass metabolism. Therefore, the computed  $F_a$  should be considered an approximation. There is no safety concern at time of discharge of Cohort 2 given that only a microtracer is dosed in this study.

Feces in Cohort 2 will be collected and will be assayed only after mass balance of [ $^{14}\text{C}$ ]PF-07220060 from Cohort 1 and urinary radioactivity data from Cohort 2 is available and only if the study team determines that analysis of total radioactivity from feces of Cohort 2 would further inform disposition of PF-07220060 in humans.

To aid in the future development of a potential pediatric dosage form of PF-07220060, the current study will assess the taste attributes of the liquid formulation immediately after (within 1 mins) and over 20 mins post oral dose administration in both cohorts.

Banked biospecimens in both cohorts will be collected and stored for future exploratory analyses. Pharmacogenomic samples from both cohorts will be collected and analyzed for the purpose of assessing the impact of allelic variants of genes encoding metabolic enzymes such as CYP3A and UGT2B7 (the major metabolizing enzymes involved in the metabolism of PF-07220060 [Section 2.2.2]).

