2.3. Study Design

This study will be a Phase 1, randomized, open-label, parallel-group, single-dose study of PF-07220060 to characterize the metabolic profile and routes of excretion for oral [^{14}C]PF-07220060 and to evaluate the absolute oral bioavailability (F) of PF-07220060 and fraction absorbed (F_a) of [^{14}C]PF-07220060, in reference to IV microtracer [^{14}C]PF-07220060 in fasted healthy male participants.

Approximately 6 healthy adult male participants will be enrolled in each of the 2 cohorts. Participants in Cohorts 1 and 2 will receive treatment regimen A and B, respectively. If there are participants who withdraw or discontinue treatment and are considered to be non-evaluable with respect to the primary and secondary PK objective(s), additional participants can be enrolled at the discretion of the investigator upon consultation with the sponsor.

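### The SAP gives Fa a within-participant model and calls for Fa to be summarised by treatment, although oral and IV urine recoveries come from different people

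*SAP*

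**What the plan says.** The design is parallel. Protocol Section 1.1 (Study Arms and Duration) says: "This will be a parallel-cohort study including 2 independent cohorts without crossover". Protocol Section 4.2 draws the consequence for Fa: "Note, IV and oral radioactivities will be collected from participants in different cohorts". SAP Section 6.2.2 acknowledges the same thing, saying the data come from "different people in separate cohorts, where physiological variability may lead to a less robust estimation of" Fa. On size, SAP Section 2.3 says: "Approximately 6 healthy adult male participants will be enrolled in each of the 2 cohorts".

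For the analysis of Fa, the SAP says four things:

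- Section 6.2.2 defines the estimate as the ratio, oral over IV, of the geometric means of percent radioactive dose in urine. It mentions no interval.
- Section 6.2.2 then says that cumulative amounts, percent dose and Fa "will be listed by treatment (Oral in Cohort 1 and IV in Cohort 2) and summarized using descriptive statistics".
- Appendix 1 gives the method as "Mixed effect model or Hodges-Lehmann point estimate".
- Appendix 2 gives Fa the same model statements as absolute bioavailability (F): treatment as fixed effect, Kenward-Roger degrees of freedom, "random participant / subject=participant", and a 90% interval for the contrast.

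Protocol Section 9.3.2.1 specifies a mixed model for F. Section 9.3.2.2 gives only a ratio of geometric means, with an optional Hodges-Lehmann estimate, for Fa. SAP Section 2.1 declares no changes from the protocol.

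**The concern.** The random participant effect suits F, because each Cohort 2 participant supplies both an oral and an IV exposure. It does not suit Fa, where each participant supplies one cumulative recovery on one route. With one value per person, nothing in the data distinguishes variation between participants from residual variation.

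The descriptive summary has a related problem. SAP Table 3 defines Fa as an oral total over an IV total, adjusted for dose. No participant has both totals, and the SAP names neither a matching rule nor a fixed IV reference value. A listing of Fa by treatment, and a mean or SD of it, therefore has no defined content.

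Fa is a secondary endpoint, and Protocol Section 4.1 compares F and Fa with 0.9 to classify permeability. A reader of the study report will want to know how precisely Fa was estimated. The plan leaves that to the software's treatment of a model that is not identified.

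**Working it through.** The documents give no precision figure for Fa, so there is nothing to reproduce. The check is whether the Appendix 2 model is identified, and what it implies for the ratio and its interval.

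**Inputs.** Six participants per cohort (SAP 2.3), one log percent recovery each (SAP Table 3), 90% interval (alpha = 0.1 in Appendix 2).

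**Step 1: the model.** Write log recovery = treatment mean + participant effect (variance P) + residual (variance R). With one value per person, every observation has variance P + R and all 12 are independent. The likelihood depends on P and R only through their sum.

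**Step 2: numerical confirmation.** Simulated log recoveries were used for 6 + 6 people (true medians 40% IV and 30% oral, log SD 0.3; illustrative only). The pooled variance was 0.03686.

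- The REML log-likelihood was 9.7117 with 0%, 25%, 50%, 75% or 99% of the variance assigned to participant.
- All four entries of the information matrix for (P, R) equal 5/0.03686² ≈ 3681, so its determinant is 0 and its rank is 1 of 2.
- In the paired layout used for F (6 people, 2 values each), the rank is 2. The same code is valid there.

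**Step 3: the ratio.** The fixed-effect design has full rank. For every variance split the estimate was −0.301 on the log scale, a ratio of 0.740, with standard error √(0.03686 × 2/6) = 0.111. This is the two-sample result. With t(0.95, 10) = 1.812, the 90% interval is exp(−0.301 ± 1.812 × 0.111) = 0.605 to 0.905.

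**Step 4: degrees of freedom.** Kenward-Roger needs the inverse of the information matrix, which does not exist here. Suppose software substitutes a generalised inverse. With c the common entry of the matrix, the variance of the squared standard error is 1/(9c). The degrees of freedom are then 2 × (0.03686/3)² × 9c = 2 × 0.03686² × c = 10. That reproduces the two-sample interval.

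**Step 5: what software can do.** The same random-intercept model was fitted to the simulated data in Python's statsmodels. It warned that the Hessian was not positive definite, split the variance 50/50 arbitrarily, and reported a standard error of 0.040. That is 0.040/0.111 = 36% of the correct value. PROC MIXED was not run, so its behaviour is not established.

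**Step 6: what the unpaired analysis delivers.** The factor by which the ratio is multiplied and divided is exp(1.812 × s × √(2/6)), with s² = ln(1 + CV²). The documents give no variability for urine recovery. Protocol Section 2.2.4.3 gives 11–77% for steady-state Cmax in monotherapy cohorts, used here only as a range of assumptions. At Fa = 0.90:

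- CV 11%: factor 1.12, interval 0.80 to 1.01
- CV 30%: factor 1.36, interval 0.66 to 1.22
- CV 77%: factor 2.04, interval 0.44 to 1.84

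These widths reflect six people per cohort. They do not measure the coding error. They show why the interval should be reported from a properly specified model.

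**The case against.** The best defence is that the random statement is redundant rather than harmful. The ratio and its model-based standard error are the same for every variance split, and a generalised inverse gives 10 degrees of freedom and the correct interval. The code is offered as an example, Section 6.2.2 already specifies a between-cohort ratio, no hypothesis is tested, and the 0.9 rule in Protocol Section 4.1 uses the estimates themselves. Both documents also acknowledge that Fa is approximate or less robust. All of this stands, and it limits the severity. It does not remove the singular fit, which Appendix 1 repeats by naming a mixed model, and it does not define an individual Fa.

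A reader might infer more than the documents support:

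- **That Fa itself cannot be estimated.** It can; only the two variance components are inseparable.
- **That the code would return 1/Fa.** SAP Section 2.3 says "Participants in Cohorts 1 and 2 will receive treatment regimen A and B, respectively", so A is the oral-label cohort there, while the Fa code uses A for IV. But the code comment defines its own letters, and Section 6.2.2 independently fixes IV as reference and oral as test. The F code uses A and B for two treatments given to the same Cohort 2 participants, so the letters are not regimen codes.
- **That the sponsor plans to pair people across cohorts.** No passage proposes this. The listing sentence may simply be loose wording for a single cohort-level value; the defect is that it does not say so.
- **That Section 6.2.2 and Appendix 2 conflict over the interval.** Section 6.2.2 is silent and the code supplies one. The text needs completing.

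**Conclusion.** The point holds at moderate severity. The Fa model in Appendix 2, and the method named in Appendix 1, suit paired data that this design does not produce. The fit is singular by construction. The point estimate of Fa does not change. The 90% interval is right or wrong according to how the software resolves the singularity: a generalised inverse gives the correct 10-degree-of-freedom result, while one program tested gave a standard error about a third of the correct one. Whether PROC MIXED would fail, warn or give the correct interval is not known from this check.

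The participant-level Fa summary is undefined whatever the software does, because SAP Table 3 needs two totals that no one person has.

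The algebra rests on one cumulative recovery per participant. The 10 degrees of freedom also assume six evaluable participants per cohort and a common variance. The interval widths rest on assumed CVs.

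**What to change.** - **Appendix 2:** delete the random statement from the Fa code. Fit an unpaired model to log percent radioactive dose in urine with treatment as the only fixed effect. Pooled variance gives 6 + 6 − 2 = 10 degrees of freedom. Separate variances by cohort is an acceptable alternative; state which is used. Leave the F code as it is.
- **Appendix 1:** replace the mixed effect model for Fa with this two-sample model. If Hodges-Lehmann is kept, specify the two-sample version on the log scale, based on the 6 × 6 = 36 oral-minus-IV differences.
- **Section 6.2.2:** state that Fa is one between-cohort ratio of geometric means, reported with its 90% interval. List and summarise percent dose in urine by participant and cohort, and remove Fa from the participant-level listing and summary.

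The cost is a few lines of SAP text and code before analysis. No data collection, sample size or endpoint definition changes.
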